Appendix C: Oral PrEP Arm Instruments

Activity Title: Baseline Information About You

Activity Description: Today we'll ask you to answer some questions about yourself. The survey is 17 questions and should take about 10 minutes to complete.

Baseline Demographic Survey

Question	Question #
What year were you born? [Write in]	1
Which of the following best describes your racial/ethnic background? (Select all that apply) 
  African American/Black  Asian/Pacific Islander  Caucasian/White  Hispanic/Latinx  Native American/Alaska Native  A race or ethnicity not listed: [Write in] 	2
How do you describe your gender? (Select 1) 
  Female  Male  Transgender woman  Transgender man  Non-binary  A gender not listed: [Write in] 	3
How do you describe your sexual orientation? (Select 1) 
  Heterosexual/Straight  Gay or Lesbian  Bisexual  Queer or Sexually Fluid  Pansexual  A sexual orientation not listed: [Write in] 	4
What is the highest degree or school level you have completed? (Select 1) 
  Primary school  Some high school  High school diploma or GED  Some college  2-year college degree  4-year college degree  Graduate level degree  An school level not listed: [Write in] 	5
What health coverage are you currently enrolled with? (Select up to 2) 
  Medicaid  Medicare  Affordable Care Act  Uninsured  Private health insurance 	6

 A health coverage not listed: [Write in]	
Why are using pre-exposure prophylaxis (PrEP) to prevent HIV? [Select all that apply]  Reduce acquisition of HIV from sex  Reduce acquisition of HIV from IV drug use	7
The next 5 questions ask about your food, housing, and transportation routines from the past 12 months. If you have concerns and need support, please check in with your provider at your next visit or call 2-1-1 for immediate support.	
In the last 12 months, was there a time when you were not able to pay the mortgage or rent on time?  No  Yes  Not applicable	8
In the last 12 months, was there a time when you did not have a steady place to sleep or slept in a shelter (including now)?  No  Yes	9
In the last 12 months, have you or the people you live with been unable to get utilities (heat, electricity) when it was really needed?  No  Yes	10
Within the past 12 months, the food you bought just didn't last and you didn't have money to get more.  Never true  Sometimes true  Often true	11
Within the past 12 months, has lack of transportation kept you from medical appointments, getting your medicines, non-medical meetings or appointments, work, or from getting things that you need?  No  Yes	12
Do you feel physically and emotionally safe where you currently live?  Yes  No	13
During the past 30 days, have you used any of the following? 
 • An illegal drug (such as by snorting it or injecting it) • Pain killer to get high (like OxyContin, sometimes called Oxy or OC) or Percocet (sometimes called Percs) • Prescription drugs not prescribed to you  No  Yes	14

People who experience discrimination may be at higher risk of negative health outcomes. Sharing your experiences with discrimination in everyday life and in healthcare settings may help researchers learn how to reduce negative health outcomes associated with discrimination.
 
The next 3 statements describe how others may treat you.
	

In your day-to-day life, how often do any of these happen to you?	
You are treated with less respect than other people are. 
  Never  Less than once a year  A few times a year  A few times a month  At least once a week  Almost every day 	15
People act as if they're better than you. 
  Never  Less than once a year  A few times a year  A few times a month  At least once a week  Almost every day 	16
What do you think is the main reason for these experiences? (Select 1) 
  Your gender  Your sexual orientation  Your race  Your religion  Some aspect of your physical appearance  Your education or income level  Other: [Write in] 	17

End Message: Thank you for completing this survey!

Persistence Assessment

Activity Title: Are You Still Taking PrEP?

Activity Description: In this short survey, we'll ask you some questions about your PrEP journey and any challenges you may have encountered.

Activity:

1. Are you still taking PrEP medicine by mouth?

- Yes, I am taking PrEP (branching logic to question 4)
- No, I stopped taking PrEP (branching logic to questions 2)

2. Over the past week, how many days did you miss taking PrEP?

- 0
- 1
- 2
- 3
- 4
- 5
- 6

7

3. If you stopped taking PrEP, which of the following best describes the reason(s) why? [Select up to 2]

- I no longer feel I needed to take PrEP (branching logic to question 3 if selected)
- It was too difficult to take PrEP with my schedule
- I did not want people to know I was taking it or I felt I was being judged by others for taking PrEP
- I did not like the side effects
- I take too many medications
- There were too many appointments as part of my PrEP care
- I tested positive for HIV
- Other: [Fill in the blank]

4. Which of the following best describes why you no longer feel you need to take PrEP?

- I am no longer having sex
- I am in a monogamous relationship
- I am no longer using injectable drugs
- My partners and I are all regularly using condoms and getting tested for HIV
- Other: [Fill in the blank]

5. If you are still taking PrEP, what challenges have you experienced? [Select up to 2]

- Have not experienced any challenges
- Remembering to take PrEP every day
- Keeping up with clinical visits and laboratory testing
- Concerns about side effects
- Finding transportation to my appointments
- Stigma or discrimination from family, friends, or partner(s)
- Stigma or discrimination from healthcare professionals
- Other: [Fill in the blank]

6. Did a healthcare provider (for example, a doctor, nurse, or pharmacist) or navigator ever ask you what may make it difficult for you to take PrEP?

- Yes
- No
- Unsure

End Message: Thank you for completing this survey!

Patient Reported Outcomes – Set 1

Activity Title: Your Experiences with PrEP

Activity Description: This month we'll ask you to answer questions about your experience using PrEP and your thoughts about PrEP-related stigma. We'll also ask some questions about your experience using this mobile app to support you taking PrEP. The survey is 3 parts with a total of 24 questions. It should take you 10-15 minutes to complete.

Activity:

Part 1. Tell us about your experience using PrEP

The following questions are related to the PrEP medicine you use to protect you from HIV infection and your experience over the **past 4 weeks**. Please answer each question by selecting a number on each of the scales.

1. How satisfied are you with your **current medicine** for PrEP?
 - Very satisfied
 - Satisfied
 - Neither satisfied or dissatisfied
 - Dissatisfied
 - Very dissatisfied
2. How **bothered** are you by any **side effects** from the medicine you use for PrEP?
 - Very unbothered
 - Unbothered
 - Neither unbothered or bothered
 - Bothered
 - Very bothered
 - I have not experienced any side effects in the last 4 weeks
3. How satisfied are you with the **convenience** of PrEP recently?
 - Very satisfied
 - Satisfied
 - Neither satisfied or dissatisfied
 - Dissatisfied
 - Very dissatisfied
4. How satisfied are you with the **discreetness** of PrEP recently?
 - Very satisfied
 - Satisfied
 - Neither satisfied or dissatisfied
 - Dissatisfied
 - Very dissatisfied
5. How satisfied are you with your **understanding of using PrEP** to prevent HIV?
 - Very satisfied
 - Satisfied

- Neither satisfied or dissatisfied
- Dissatisfied
- Very dissatisfied
6. How satisfied are you with the extent to which PrEP **fits in with your lifestyle?**
- Very satisfied
- Satisfied
- Neither satisfied or dissatisfied
- Dissatisfied
- Very dissatisfied
7. Would you recommend this type of PrEP to someone else who wants to protect themselves from HIV?
- Yes, I would **definitely recommend** this type of PrEP
- Yes, I would **recommend** this type of PrEP
- Not sure if I would recommend or not recommend this type of PrEP
- No, I would **not recommend** this type of PrEP
- No, I would **definitely not recommend** this type of PrEP
8. How satisfied would you be to continue your present form of PrEP?
- Very satisfied
- Satisfied
- Neither satisfied or dissatisfied
- Dissatisfied
- Very dissatisfied

Part 2. What are your thoughts about PrEP-related stigma?

Stigma is a negative and unfair belief about someone because of a particular characteristic or attribute. Please answer the following statements to the best of your ability.

Indicate how much you agree with the following:

	Completely agree	Agree	Neither Agree or Disagree	Disagree	Completely disagree
I feel ashamed to take PrEP pills in front of others.	()	()	()	()	()
People experience negative judgment because they take PrEP.	()	()	()	()	()

Someone taking PrEP should keep their pills hidden.	()	()	()	()	()
---	-----	-----	-----	-----	-----

	Completely agree	Agree	Neither agree or disagree	Disagree	Completely disagree
Someone taking PrEP would be seen by others as slutty.	()	()	()	()	()
People taking PrEP receive praise for being responsible.	()	()	()	()	()
My friends would be supportive of me taking PrEP.	()	()	()	()	()

	Completely agree	Agree	Neither agree or disagree	Disagree	Completely disagree
Someone taking PrEP would be treated unfairly by their doctors.	()	()	()	()	()
People experience problems when they tell their sex partner(s) they are taking PrEP.	()	()	()	()	()
I feel proud to take PrEP.	()	()	()	()	()

	Completely agree	Agree	Neither agree or disagree	Disagree	Completely disagree
People on PrEP are taking care of their health.	()	()	()	()	()
My family would be supportive of me taking PrEP.	()	()	()	()	()

Part 3. What is your experience using the TheraPay mobile app?

Please assess your experience using the TheraPay mobile app to support you in your journey using PrEP.

	Completely agree	Agree	Neither agree nor disagree	Disagree	Completely disagree
1. The TheraPay mobile app meets my approval.	1	2	3	4	5
2. The TheraPay mobile app is appealing to me.	1	2	3	4	5
3. I like the TheraPay mobile app.	1	2	3	4	5
4. I welcome the TheraPay mobile app.	1	2	3	4	5

Patient Reported Outcomes – Set 2

Activity Title: Your Experiences With PrEP

Activity Description: This month we'll ask you to answer questions about your experience using PrEP (pre-exposure prophylaxis). We'll also ask some questions about your experience using this mobile app to support you taking PrEP. The survey is two parts with a total of 16 questions. It should take you 8-12 minutes to complete.

Part 1. Tell us about your experience using PrEP

Question	Question # Oral PrEP Arm [13]	Sub-concept
Over the past 4 weeks, how confident were you that PrEP prevented you from acquiring HIV ?  Very confident  Quite confident  Somewhat confident  A little confident  Not at all confident	1	Perceived efficacy
[Oral PrEP arm] Over the past 4 weeks, did you experience any side effects from the PrEP pill?  No (branching logic to question 5)  Yes (branching logic to show 3)	2	Acceptance of side effects
Over the past 4 weeks, how acceptable or unacceptable did you find the side effects from PrEP?  Very acceptable  Acceptable  Neither acceptable or unacceptable  Unacceptable  Very unacceptable	3 (branching logic)	Acceptance of side effects
Over the past 4 weeks, did the side effects of the PrEP medication interfere with your physical activity (such as lifting things, walking, jogging), your leisure or free time activities (such as gardening, reading, dancing, visiting friends), or your daily activities (such as shopping, working, house work, yard work)?  No, not at all	4 (branching logic)	Acceptance of side effects

 Yes, a little  Yes, somewhat  Yes, quite a bit  Yes, very much		

[Oral PrEP arm] Over the past 4 weeks, did you ever feel like you needed to hide your PrEP pills so others would not see them?
  No, not at all  Yes, occasionally  Yes, often  Yes, quite often  Yes, all the time	5	N/A

[Oral PrEP arm] Over the past 4 weeks, how acceptable or unacceptable did you find the time it took to take your PrEP pill every day?
  Very acceptable  Acceptable  Neither acceptable or unacceptable  Unacceptable  Very unacceptable	6	Convenience

[Oral PrEP arm] Over the past 4 weeks, how acceptable or unacceptable did you find the number of times you had to take your PrEP pill?
  Very acceptable  Acceptable  Neither acceptable or unacceptable  Unacceptable  Very unacceptable	7	Convenience

[Oral PrEP arm] Over the past 4 weeks, how easy or difficult was it to remember to take your PrEP pills?
  Very easy  Easy  Neither easy or difficult  Difficult  Very difficult	8	Convenience

[Oral PrEP arm] Over the past 4 weeks, how easy or difficult was it to fit in taking the PrEP pill into your daily life?
  Very easy  Easy  Neither easy or difficult  Difficult  Very difficult	9	Convenience

Over the past 4 weeks, how convenient or inconvenient did you find taking the PrEP?
  Very convenient	10	Convenience

 Convenient  Neither convenient or inconvenient  Inconvenient  Very inconvenient		
[Oral PrEP arm] In the future, would you choose to continue using the PrEP pill to protect yourself from HIV infection?  Yes, definitely  Yes, probably  I don't know  Probably not  Definitely not	11	Overall Acceptance
[Oral PrEP arm] In the future, would you choose to switch to using the PrEP injection to protect yourself from HIV infection?  Definitely not  Probably not  I don't know  Yes, probably  Yes, definitely	12	Overall Acceptance
Thinking about all aspects of using PrEP over the past 4 weeks, how acceptable or unacceptable did you find the medicine?  Very acceptable  Acceptable  Neither acceptable or unacceptable  Unacceptable  Very unacceptable	13	Overall Acceptance
Overall, over the past 4 weeks, how acceptable or unacceptable did you find taking all of your medicines, including PrEP and any other pills, tablets, or injections ?  Very acceptable  Acceptable  Neither acceptable or unacceptable  Unacceptable  Very unacceptable	14	Overall Acceptance

Part 2. What is your experience using this mobile app?

Please assess how **appropriate** the use of a mobile app has been to support you in your journey using PrEP.

	Completely agree	Agree	Neither agree nor disagree	Disagree	Completely disagree
1. Using a mobile app to support me using PrEP seems fitting.	1	2	3	4	5

2. Using a mobile app to support me using PrEP seems suitable.	1	2	3	4	5
3. Using a mobile app seems applicable.	1	2	3	4	5
4. Using a mobile app to support me using PrEP seems like a good match.	1	2	3	4	5

[figure not shown]
End Message: Thank you for completing this survey! We will ask you these same questions again later to see how your responses have changed.

Health Literacy Evaluation - Month 2

Activity Description: Was the pop quiz on PrEP medicine helpful? What did you learn?

Activity:

1. How helpful was the pop quiz reviewing important facts about PrEP?

2. True/False: A person who takes PrEP will also need to use condoms to prevent other STIs.

- True**
 - That's correct! PrEP only protects against HIV. Condoms will protect you against other sexually transmitted infections, such as syphilis, gonorrhea, or chlamydia. Condoms will also protect against unintended pregnancy.
- False**
 - Not quite. PrEP only protects against HIV. Condoms will protect you against other sexually transmitted infections, such as syphilis, gonorrhea, or chlamydia. Condoms will also protect against unintended pregnancy.

Health Literacy Evaluation – Month 4

Activity Description: Was the video on protecting yourself helpful? What did you learn?

Activity:

1. How helpful was the video on sexual health, safer IV drug use, and protecting yourself?

2. True/False: All body parts used for sex should be tested for HIV & sexually transmitted infections (STIs).

True

That's correct! In many cases, this means you should have three body parts tested – (1) the throat; (2) the front (vagina, front hole, penis, urethra); and (3) the back (anus and rectum).

False

Not quite. All body parts used for sex should be tested for STIs. In many cases, this means you should have three body parts tested – (1) the throat; (2) the front (vagina, front hole, penis, urethra); and (3) the butt hole and rectum.

3. True/False: All sexually transmitted infections (STIs) will cause symptoms.

a. True

Not quite. Many STIs do not cause any symptoms that you would notice. It is important to get regular testing.

b. False

[figure not shown]
That's correct! Many STIs do not cause any symptoms that you would notice. It is important to get regular testing.

Health Literacy Evaluation – Month 6

Activity Description: Was the video on “Building a Support System for HIV Prevention” helpful? What did you learn?

Activity:

1. How helpful was the video on building your support system?

2. True/False: West Virginia Health Right has services available if you are facing stressors or challenges.

True

That's right! There are many services available including telehealth appointments, health education classes, support for alcohol or drug addiction, LGBTQIA+ health, help from social workers, family planning services, dental and vision care, primary health care, behavioral or mental health care, pharmacy, and testing and screening for different health concerns. You can contact WVHR at [contact] for more information.

False

Not quite. There are many services available including telehealth appointments, health education classes, support for alcohol or drug addiction, LGBTQIA+ health, help from social workers, family planning services, dental and vision care, primary health care, behavioral or mental health care, pharmacy, and testing and screening for different health concerns. You can contact WVHR at [contact] for more information.

3. True/False: A support person could be a partner, family member, friend, peer navigator, or social worker.

True

That's correct. Any one of these people could help support you. It's your choice and completely up to you who you want to bring on your support team.

False

[figure not shown]
Not quite. Any one of these people could help support you. It's your choice and completely up to you who you want to bring on your support team.

Health Literacy Evaluation – Month 8

Activity Description: Was the article on “Being an Active Participant in Your Own Care” helpful? What did you learn?

Activity:

1. How helpful was the article on being an active participant in your own care?

2. Which of the following best describes shared decision-making?

- When your doctor makes a decision about your healthcare that they feel is in your best interest**

Not quite. Shared decision-making is a process where you and your healthcare providers work together to make decisions that reflect what's most important to you while making sure your medications are safe and effective.

- When you and your doctor work together to make a decision about your healthcare that considers your values, goals and concerns**

That's right! Shared decision-making is a process where you and your healthcare providers work together to make decisions that reflect what's most important to you while making sure your medications are safe and effective.

- When your doctor works with another member of the care team (such as a nurse or social worker) to make a decision about your healthcare**

Not quite. Shared decision-making is a process where you and your healthcare providers work together to make decisions that reflect what's most important to you while making sure your medications are safe and effective.

3. True/False: Asking questions during your appointments is an important part of shared decision-making.

- True**

That's right! By asking your healthcare provider questions, you can get all of the information you need to make decisions about your health.

- False**

Not quite. By asking your healthcare provider questions, you can get all of the information you need to make decisions about your health.

Health Literacy Evaluation – Month 8

Activity Description: Was the video on “Overcoming Stigma and Becoming a Health Advocate” helpful? What did you learn?

Activity:

1. How helpful was the video on overcoming stigma and becoming a health advocate?

2. True/False: Stigma is when someone views a person or themselves in a negative way because of their unique identity, circumstances, and/or experiences.

- True**

That's right! Stigma is a negative and unfair belief about someone because of a particular characteristic or attribute.

- False**
Not quite. Stigma is a negative and unfair belief about someone because of a particular characteristic or attribute.

3. True/False: Sharing your experience with PrEP can help fight stigma surrounding it.

- True**
That's right! Calling out biases and finding support within a community can help break the stigma cycle.
- False**
Not quite. Calling out biases and finding support within a community can help break the stigma cycle.

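### As printed, the oral Persistence Assessment routes current PrEP users past its only missed-days question, so self-reported oral adherence would come only from people who say they have stopped

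*Combined protocol and SAP*

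**What the plan says.** **The form.** Question 1 of the oral Persistence Assessment (Appendix C) asks whether the participant still takes PrEP by mouth. Its two answers carry these instructions:

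- "Yes, I am taking PrEP (branching logic to question 4"
- "No, I stopped taking PrEP (branching logic to questions 2"

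The later questions are:

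- Question 2: "Over the past week, how many days did you miss taking PrEP", answered 0 to 7.
- Question 3: reasons for stopping. Its first option reads "I no longer feel I needed to take PrEP (branching logic to question 3 if selected".
- Question 4: "Which of the following best describes why you no longer feel you need to take PrEP".
- Question 5: "If you are still taking PrEP, what challenges have you experienced? [Select up to 2".
- Question 6: whether a provider or navigator asked about difficulties.

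Section 6.2 has oral participants complete this assessment monthly, months 1 to 12, and has patients complete assessments in the TheraPay App.

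**The analysis.** Section 6.2.7.1 A assesses oral adherence at months 3 and 12 by the number of people reporting at least three missed days, with the mean and median days missed. Section 7 sets that proportion against missed injections in the CAB-LA arm and calls adherence a co-primary endpoint. Neither section names the item that supplies the oral count.

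**The concern.** The skip instructions do the reverse of what the adherence measure needs. A person still taking pills is the one whose missed days matter, and that person jumps over the missed-days item to a question that can apply only to someone who has stopped. The person who has stopped is asked how many days were missed last week.

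If the app behaves this way, there are two ways to go wrong at analysis. Using only the answers present makes the oral adherence result a description of stoppers, which largely repeats non-persistence, although 6.2.2.1 defines persistence as independent of adherence. Reading a blank as no missed days makes every current user look adherent. Neither result measures adherence among people taking oral PrEP.

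**Working it through.** **1. Compare the two arms' forms.**

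| | CAB-LA form (Appendix B) | Oral form (Appendix C) |
|---|---|---|
| Question 1, Yes goes to | 4 | 4 |
| Question 1, No goes to | 2 | 2 |
| Option that PrEP is no longer needed goes to | 3 | 3 |
| Question 2 | Reasons for stopping | Days missed, past week |
| Question 3 | Why no longer needed | Reasons for stopping |
| Question 4 | Challenges, current users | Why no longer needed |
| Question 5 | Provider asked about difficulties | Challenges, current users |
| Question 6 | none | Provider asked about difficulties |

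The three targets are identical. All three work in the CAB-LA form. In the oral form, which has one more item at question 2, none reaches the question it should, and the option inside question 3 points to question 3 itself. The targets appear not to have been updated for the extra item.

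**2. Trace the printed paths.** A current user goes from question 1 to question 4 and never meets question 2. A person who has stopped goes from question 1 to question 2.

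**3. Look for another source of missed days in the oral instruments.** There are two near candidates. Question 5 offers "Remembering to take PrEP every day" as a challenge. Item 8 of Patient Reported Outcomes Set 2 asks "how easy or difficult was it to remember to take your PrEP pills". Neither gives a number of days. That question 2 feeds 6.2.7.1 A and Section 7 is therefore an inference, but no other item could.

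**4. The plan's own figure.** Section 7 (Sample Size) takes adherence proportions of .90 and .65 with 70 and 35 participants:

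- SE = √(.90 × .10/70 + .65 × .35/35) = .08824
- .25 ± 1.96 × .08824 = .0771 to .4229, as stated.

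The interval assumes all 35 oral participants contribute. The text does not say which adherence contrast it describes. It is not recomputed on the reduced numbers, because there is no reason to apply .65 to people who have stopped.

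**5. Size if the app follows the form.** Someone on oral PrEP throughout supplies 0 of 12 monthly missed-days answers. The documents give no oral persistence rate, so a range is assumed, with everyone responding:

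| Still on oral PrEP | × 35 | Current users with no answer | Stoppers who reach question 2 |
|---|---|---|---|
| 50% | 17.5 | about 18 | about 17 |
| 65% | 22.75 | 23 | 12 |
| 80% | 28 | 28 | 7 |
| 90% | 31.5 | 32 | 3 |

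At 50% the split could equally be rounded to 17 and 18. The last column also requires every stopper to keep completing the survey.

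**The case against.** The strongest reply is that the harm is conditional. Patients answer in an app whose programmed logic is not in the documents, and the printed routing fails so visibly that building or testing it would probably have exposed the fault. That stands. The printed error is certain; the data loss is not.

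A reader might infer that the primary endpoint has no oral data. The documents do not support this:

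- The Study Outcomes Table labels its primary endpoint adherence and persistence but defines it by continued receipt of injections or use of oral PrEP. Oral question 1 supplies that, and every participant is asked it.
- The possession ratio and the 90-day gap (6.2.7.1 B) rest on dispensing records.
- The documents disagree about the status of adherence. Section 7, 3.2.1 and the Appendix G schema give it primary standing, while the protocol summaries name persistence only.

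A reader might also infer that no current user could ever have a missed-days answer. That holds only assessment by assessment: someone who reported stopping one month and later resumed would have an answer from the month off PrEP.

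Finally, nothing records the order in which the forms were drafted, so failure to renumber is the likely cause, not a documented one. Who belongs in the adherence denominator, and where the CAB-LA missed-injection count comes from, are separate questions and no part of this point.

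**Conclusion.** The form is wrong as written and should be corrected. Under the printed routing, no participant who reports being on oral PrEP at a given assessment supplies a missed-days answer at that assessment. The measure in 6.2.7.1 A, and the oral side of the first adherence contrast in Section 7, would come only from people who report having stopped. On the assumed 50% to 90% still on PrEP, with full response, about 18 to 32 of 35 would be without an answer at a landmark.

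This rests on two things the documents do not settle: that the app follows the printed form, and that question 2 is the intended source. Self-reported persistence and both dispensing-based measures stand either way.

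**What to change.** **Appendix C, oral Persistence Assessment.**

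- Question 1, Yes: go to question 2, then 5, then 6.
- Question 1, No: go to question 3.
- Question 3, first option: go to question 4, then 6.
- Question 3, all other options: go straight to question 6.

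**App.** Check the deployed logic against this and correct it if it follows the printed form.

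**Sections 6.2.7.1 A and 7.** Name question 2 as the source of oral missed days. State that it covers the past week at the month 3 and month 12 assessments. Treat a current user with no answer to it as missing, not as adherent. If the app has already run as printed, report that self-reported oral adherence is unavailable for current users at the affected assessments.

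**Cost.** Corrected jump targets, a check of the app with small reprogramming if needed, and a few sentences of text; no extra visits or participants. Answers already skipped cannot be recovered from this survey. Stating the window will also make plain that the oral count covers single weeks while Section 7 counts CAB-LA missed injections over the whole study period; this change does not remove that difference.
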